12.2.3 Methods for Evaluation of Measurable Disease

All measurements should be taken and recorded in metric notation using a ruler or calipers.

The same method of assessment and the same technique should be used to characterize each identified and reported lesion at baseline and during follow-up. Imaging-based evaluation is preferred to evaluation by clinical examination unless the lesion(s) being followed cannot be imaged but are assessable by clinical exam.

- 12.2.3.1 Clinical lesions: Clinical lesions will only be considered measurable when they are superficial (e.g., skin nodules and palpable lymph nodes) and ≥ 10 mm diameter as assessed using calipers (e.g., skin nodules). In the case of skin lesions, documentation by color photography, including a ruler to estimate the size of the lesion, is recommended.
- 12.2.3.2 Chest x-ray: Lesions on chest x-ray are acceptable as measurable lesions when they are clearly defined and surrounded by aerated lung. However, CT is preferable.
- 12.2.3.3 Conventional CT and MRI: This guideline has defined measurability of lesions on CT scan based on the assumption that CT slice thickness is 5 mm or less. If CT scans have slice thickness greater than 5 mm, the minimum size for a measurable lesion should be twice the slice thickness. MRI is also acceptable in certain situations (e.g. for body scans). Ideally, the same type of scanner should be used and the image acquisition protocol should be followed as closely as possible to prior scans.
- 12.2.3.4 PET-CT: At present, the low dose or attenuation correction CT portion of a combined PET-CT is not always of optimal diagnostic CT quality for use with RECIST measurements. However, if the site can document that the CT performed as part of a PET-CT is of identical diagnostic quality to a diagnostic CT (with IV and oral contrast), then the CT portion of the PET-CT can be used for RECIST measurements and can be used interchangeably with conventional CT in accurately measuring cancer lesions over time. Note, however, that the PET portion of the CT introduces additional data which may bias an investigator if it is not routinely or serially performed.
- 12.2.3.5 Tumor markers: Tumor markers alone cannot be used to assess response. If markers are initially above the upper normal limit, they must normalize for a patient to be considered in complete clinical response.
- 12.2.3.6 Cytology, Histology: These techniques can be used to differentiate between partial responses (PR) and complete responses (CR) in rare cases (e.g., residual lesions in tumor types, such as germ cell tumors, where known residual benign tumors can remain).

Cytology should be obtained if an effusion appears or worsens during treatment when the measurable tumor has met criteria for response or stable disease.

- 12.2.3.7 FDG-PET: While FDG-PET response assessments need additional study, it is sometimes reasonable to incorporate the use of FDG-PET

THIS PROTOCOL IS FOR RESEARCH PURPOSES ONLY, SEE PAGE 1 FOR USAGE POLICY

scanning to complement CT scanning in assessment of progression (particularly possible 'new' disease). New lesions on the basis of FDG-PET imaging can be identified according to the following algorithm:

- a. Negative FDG-PET at baseline, with a positive FDG-PET at follow-up is a sign of PD based on a new lesion.
- b. No FDG-PET at baseline and a positive FDG-PET at follow-up: If the positive FDG-PET at follow-up corresponds to a new site of disease confirmed by CT, this is PD. If the positive FDG-PET at follow-up is not confirmed as a new site of disease on CT, additional follow-up CT scans are needed to determine if there is truly progression occurring at that site (if so, the date of PD will be the date of the initial abnormal FDG-PET scan). If the positive FDG-PET at follow-up corresponds to a pre-existing site of disease on CT that is not progressing on the basis of the anatomic images, this is not PD.

Note: A 'positive' FDG-PET scan lesion means one that is FDG avid with an uptake greater than twice that of the surrounding tissue on the attenuation corrected image.

12.2.4 Response Criteria for Patients with Solid Tumor and Measurable Disease

12.2.4.1 **Evaluation of Target Lesions**

Complete Response (CR): Disappearance of all target and non-target lesions. Any pathological lymph nodes (whether target or non-target) must have reduction in short axis to <10 mm. If immunocytology is available, no disease must be detected by that methodology. Normalization of urinary catecholamines or other tumor markers if elevated at study enrollment (for patients with neuroblastoma).

Partial Response (PR): At least a 30% decrease in the sum of the diameters of target lesions, taking as reference the baseline sum diameters

Progressive Disease (PD): At least a 20% increase in the sum of the diameters of target lesions, taking as reference the smallest sum on study (this includes the baseline sum if that is the smallest on study). In addition to the relative increase of 20%, the sum must also demonstrate an absolute increase of at least 5 mm. (Note: the appearance of one or more new lesions is also considered progressions). Note: in presence of SD or PR in target disease but unequivocal progression in non-target or non-measurable disease, the patient has PD if there is an overall level of substantial worsening in non-target disease such that the overall tumor burden has increased sufficiently to merit

THIS PROTOCOL IS FOR RESEARCH PURPOSES ONLY, SEE PAGE 1 FOR USAGE POLICY

discontinuation of therapy

Stable Disease (SD): Neither sufficient shrinkage to qualify for PR nor sufficient increase to qualify for PD, taking as reference the smallest sum diameters while on study

12.2.4.2 Evaluation of Non-Target Lesions

Complete Response (CR): Disappearance of all non-target lesions and normalization of tumor marker level. All lymph nodes must be non-pathological in size (<10 mm short axis)

Note: If tumor markers are initially above the upper normal limit, they must normalize for a patient to be considered in complete clinical response.

Non-CR/Non-PD: Persistence of one or more non-target lesion(s) and/or maintenance of tumor marker level above the normal limits

Progressive Disease (PD): Appearance of one or more new lesions and/or *unequivocal progression* of existing non-target lesions. *Unequivocal progression* should not normally trump target lesion status. It must be representative of overall disease status change, not a single lesion increase.

12.2.5 Overall Response Assessment

Table 1: For Patients with Measurable Disease (i.e., Target Disease)

Target Lesions	Non-Target Lesions	New Lesions	Overall Response	Best Overall Response when Confirmation is Required*
CR	CR	No	CR	≥ 28 days Confirmation
CR	Non-CR/Non-PD	No	PR	≥ 28 days Confirmation
CR	Not evaluated	No	PR	
PR	Non-CR/Non-PD/not evaluated	No	PR	
SD	Non-CR/Non-PD/not evaluated	No	SD	documented at least once ≥ 28 days from baseline
PD	Any	Yes or No	PD	

THIS PROTOCOL IS FOR RESEARCH PURPOSES ONLY, SEE PAGE 1 FOR USAGE POLICY

Any	PD**	Yes or No	PD	no prior SD, PR or CR
Any	Any	Yes	PD	

* See RECIST 1.1 manuscript for further details on what is evidence of a new lesion. ** In exceptional circumstances, unequivocal progression in non-target lesions may be accepted as disease progression. Note: Patients with a global deterioration of health status requiring discontinuation of treatment without objective evidence of disease progression at that time should be reported as “symptomatic deterioration.” Every effort should be made to document the objective progression even after discontinuation of treatment.
				

Table 2: For Patients with Non-Measurable Disease (i.e., Non-Target Disease)

Non-Target Lesions	New Lesions	Overall Response
CR	No	CR
Non-CR/non-PD	No	Non-CR/non-PD*
Not all evaluated	No	not evaluated
Unequivocal PD	Yes or No	PD
Any	Yes	PD

* ‘Non-CR/non-PD’ is preferred over ‘stable disease’ for non-target disease since SD is increasingly used as an endpoint for assessment of efficacy in some trials so to assign this category when no lesions can be measured is not advised
		

Table 4: Overall Response for Patients with Neuroblastoma and Measurable Disease

CT/MRI	MIBG	Bone Scan	Bone Marrow	Catechol	Overall
PD	Any	Any	Any	Any	PD
Any	PD	Any	Any	Any	PD
Any	Any	PD	Any	Any	PD
Any	Any	Any	PD	Any	PD
SD	CR/PR/SD	Non-PD	Non-PD	Any	SD
PR	CR/PR	Non-PD	Non-PD	Any	PR
CR/PR	PR	Non-PD	Non-PD	Any	PR
CR	CR	Non-PD	Non-PD	Elevated	PR
CR	CR	CR	CR	Normal	CR

12.2.6 Overall Best Response Assessment

Each patient will be classified according to his “best response” for the purposes of analysis of treatment effect. Best response is determined as outlined in [Section 12.6](#) from a sequence of overall response assessments.

12.3 Response Criteria for Patients with Solid Tumors and Evaluable Disease

12.3.1 Evaluable Disease

The presence of at least one lesion, with no lesion that can be accurately measured in at least one dimension. Such lesions may be evaluable by nuclear medicine techniques, immunocytochemistry techniques, tumor markers or other reliable measures.

12.3.2 Complete Response

Disappearance of all evaluable disease.

12.3.3 Partial response

Partial responses cannot be determined in patients with evaluable disease

12.3.4 Stable Disease (SD)

That which does not qualify as Complete Response (CR), Partial Response (PR), or Progressive Disease.

12.3.5 Progressive Disease

The appearance of one or more new lesions or evidence of laboratory, clinical, or radiographic progression.

12.3.6 Overall Best Response Assessment

Each patient will be classified according to his “best response” for the purposes of analysis of treatment effect. Best response is determined as outlined in [Section 12.6](#) from a sequence of overall response assessments.

12.4 **Response Criteria for Neuroblastoma Patients with MIBG Positive Lesions**

12.4.1 MIBG Positive Lesions

Patients who have a positive MIBG scan at the start of therapy will be evaluable for MIBG response. The use of ¹²³I for MIBG imaging is recommended for all scans. If the patient has only one MIBG positive lesion and that lesion was radiated, a biopsy must be done at least 28 days after radiation was completed and must show viable neuroblastoma.

12.4.2 The following criteria will be used to report MIBG response by the treating institution:

Complete response:	Complete resolution of all MIBG positive lesions
Partial Response:	Resolution of at least one MIBG positive lesion, with persistence of other MIBG positive lesions
Stable disease:	No change in MIBG scan in number of positive lesions
Progressive disease:	Development of new MIBG positive lesions

[figure not shown]
12.4.3 The response of MIBG lesions will be assessed on central review using the Curie scale¹⁴ as outlined below. Central review responses will be used to assess efficacy for study endpoint. See [Section 8.2](#) for details on transferring images to the Imaging Research Center.

NOTE: This scoring should also be done by the treating institution for end of course response assessments.

The body is divided into 9 anatomic sectors for osteomedullary lesions, with a 10th general sector allocated for any extra-osseous lesion visible on MIBG scan. In each region, the lesions are scored as follows. The **absolute extension score** is graded as:

- 0 = no site per segment,
- 1 = 1 site per segment,
- 2 = more than one site per segment,
- 3 = massive involvement (>50% of the segment).

The **absolute score** is obtained by adding the score of all the segments. See diagram of sectors below:

The **relative score** is calculated by dividing the absolute score at each time point by the corresponding pre-treatment absolute score. The relative score of each patient is calculated at each response assessment compared to baseline and classified as below:

1. **Complete response:** all areas of uptake on MIBG scan completely resolved. If morphological evidence of tumor cells in bone marrow biopsy or aspiration is present at enrollment, no tumor cells can be detected by routine morphology on two subsequent bilateral bone marrow aspirates and biopsies done at least 21 days apart to be considered a **Complete Response**.
2. **Partial response:** Relative score ≤ 0.2 (lesions almost disappeared) to ≤ 0.5 (lesions strongly reduced).
3. **Stable disease:** Relative score > 0.5 (lesions weakly but significantly reduced) to 1.0 (lesions not reduced).
4. **Progressive disease:** New lesions on MIBG scan.

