5.2 Criteria for Starting Subsequent Cycles

A cycle may be repeated every 28 days if the patient has at least stable disease and has again met laboratory parameters as defined in the eligibility section, [Section 4.0](#), and is eligible to continue agent administration per the requirements in [Section 6.0](#).

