12.5 Response Criteria for Neuroblastoma Patients with Bone Marrow Involvement

12.5.1 Bone Marrow Involvement

Bone marrow obtained within 28 days prior to study enrollment with tumor cells seen on routine morphology (not by immunohistochemical staining only) of bilateral aspirate or biopsy on one bone marrow sample.

Bone Marrow responses are determined by H&E Staining of bilateral bone marrow biopsies and aspirates.

Complete Response: No tumor cells detectable by routine morphology on 2 consecutive bilateral bone marrow aspirates and biopsies performed at least 21 days apart. Normalization of urinary catecholamines or other tumor markers if elevated at study enrollment.

Progressive Disease: In patients who enroll with neuroblastoma in bone marrow by morphology have progressive disease if there is a doubling in the amount of tumor in the marrow AND a minimum of 25% tumor in bone marrow by morphology. (For example, a patient entering with 5% tumor in marrow by morphology must increase to $\geq 25\%$ tumor to have progressive disease; a patient entering with 30% tumor must increase to $> 60\%$).

In patients who enroll without evidence of neuroblastoma in bone marrow will be defined as progressive disease if tumor is detected in 2 consecutive bone marrow biopsies or aspirations done at least 21 days apart.

Stable Disease: Persistence of tumor in bone marrow that does not meet the criteria for either complete response or progressive disease.

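### Two gaps in the neuroblastoma response rules: an MIBG relative score above 1.0 without a new lesion has no central category, and marrow above 50% tumor at entry can never meet progression

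*Combined protocol and SAP*

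**What the plan says.** Section 12.4 has two MIBG scales.

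- **Institution (12.4.2), by lesion count.** Stable is "No change in MIBG scan in number of positive lesions"; partial response is "Resolution of at least one MIBG positive lesion, with persistence of other MIBG positive lesions"; progression is "Development of new MIBG positive lesions".
- **Central review (12.4.3), by Curie score.** Ten sectors are graded 0 to 3, where 3 means that more than half of the segment is involved. The total is divided by its pre-treatment value. Stable is "Relative score > 0.5 (lesions weakly but significantly reduced) to 1.0 (lesions not reduced"; progression is "New lesions on MIBG scan". This is the reading named for the efficacy endpoint. A note asks institutions to compute the score as well.

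For patients who enter with marrow disease, Section 12.5.1 requires for progression a "doubling in the amount of tumor in the marrow AND a minimum of 25% tumor in bone marrow by morphology". Stable is the remainder: "Persistence of tumor in bone marrow that does not meet the criteria for either complete response or progressive disease".

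Tables 4 and 5 combine the components. The overall SD row of Table 5 needs MIBG SD, no new CT/MRI lesion, and non-PD bone scan and marrow. The SD row of Table 4 needs CT/MRI SD, MIBG of SD or better, and non-PD bone scan and marrow. The label also enters Section 5.2: "A cycle may be repeated every 28 days if the patient has at least stable disease".

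**The concern.** The Curie grade measures extent, so a site already present at baseline can raise the score by spreading. The central categories stop at a ratio of 1.0, and the only progression criterion is a new lesion. The institutional scale does not look at extent at all. In marrow, a doubling criterion on a percentage has a ceiling: above a certain entry value it asks for more than 100%, and everything short of that falls into SD.

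What is at stake is the accuracy of the reported neuroblastoma responses. One scan can be stable (or PR) on one scale and have no category on the other. Under Section 12.6.2.2 stable disease runs until the progression criteria are met, so a criterion that cannot be met lengthens it.

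**Working it through.** **1. Reproduce the plan's marrow figures (12.5.1).** The rule amounts to a threshold of max(2 × entry %, 25%).

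- Entry 5%: max(10, 25) = 25%. The plan's example says at least 25%.
- Entry 30%: max(60, 25) = 60%. The plan's example says more than 60%.

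Both agree, although one example is inclusive and the other strict.

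**2. Apply the same rule to higher entry values.**

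| Entry | Threshold | Attainable? |
|---|---|---|
| 40% | 80% | yes |
| 49% | 98% | yes |
| 50% | 100% | only if inclusive; not under the strict sign of the 30% example |
| 51% | 102% | no |
| 60% | 120% | no |
| 80% | 160% | no |

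A rise from 60% to 95% is therefore marrow SD. In Tables 4 and 5 that counts as non-PD, so the patient is overall SD if the other components meet the SD row and none shows PD.

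**3. MIBG, growth at a constant lesion count.** Take five segments with one site each at baseline; three sites spread to more than half of their segment.

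- Baseline: 5 × 1 = 5.
- Follow-up: 3 × 3 + 2 × 1 = 11.
- Relative score: 11/5 = 2.2.

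Under 12.4.3 this is not CR, PR or SD, and it is not PD because nothing is new. Under 12.4.2 it is stable.

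**4. MIBG, mixed change.** In the same patient, one of the two unchanged sites resolves. The score is 3 × 3 + 1 × 1 + 0 = 10 and the ratio 10/5 = 2.0. Under 12.4.2 this is PR; under 12.4.3 it again has no category.

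**5. How general is the MIBG gap?** Describe a baseline by how many of the ten sectors have grade 1, 2 or 3. There are 285 non-empty patterns. Let existing sites only enlarge (1 to 3, or 2 to 3), with empty sectors staying empty. A move from 1 to 2 is excluded because it means a further site, which would normally be a new lesion. In 275 of the 285 patterns the ratio can exceed 1.0. The maximum is 3/1 = 3.0; a multi-site segment becoming massive gives 3/2 = 1.5. The other 10 patterns have every involved sector at grade 3 already. These are counts of patterns, not of patients.

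**6. What the tables do with it.** Table 5 has no row for an uncategorised MIBG result unless another component is PD. Its SD row requires MIBG SD, so the central result does not become overall SD; it is left unclassified.

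**7. Who could be affected.** Part A excludes only CNS tumors (4.1.2). The documents give no neuroblastoma count. Assume that dose confirmation closed with the six patients described in Section 2.5, and that all 6 PK expansion patients in Section 11.1 are enrolled. The upper limit is then 6 + 6 = 12, before any replacements, of whom only those with neuroblastoma matter. For known marrow disease, Section 4.1.7.1 allows at most 1 in the first six, while the PK expansion has no such limit: at most 1 + 6 = 7, and only those entering above 50% count.

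**The case against.** The strongest reply is that other rules record growth of existing disease. Marrow doubling from lower entry values is PD. A 20% (and 5 mm) increase in target lesions is PD and gives overall PD in Table 4. Bone scan PD gives overall PD in both tables. Section 12.3.5 accepts laboratory, clinical or radiographic progression without a new lesion, and 12.3.1 includes disease seen by nuclear medicine. Footnote 5 of the Section 8.1 table and Section 10.1 (a and f) let progression or removal rest on clinical judgement. The Curie score is itself recorded, so only its label is missing.

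Much of this stands. A reader might infer that the neuroblastoma rules cannot record growth at all, or that worsening always ends as overall SD. The documents support neither: the routes above exist, and an uncategorised central MIBG result does not satisfy the SD row of Table 5.

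The reply does not close the gaps:

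- CT/MRI growth helps only patients with measurable disease; in Table 5 that column records new lesions only.
- Section 12.3.5 may overlap with 12.4 for MIBG-only disease, but no precedence is stated, so the same patient could be PD under one and stable under the other.
- Section 10.1a refers back to Section 12.0 for progression.
- Central review covers only responders and patients stable for at least 6 cycles (8.2.1). The others have only the institutional reading.

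**Conclusion.** Both gaps are real and follow from the text alone. An MIBG relative score above 1.0 without a new lesion is unclassified centrally and stable, or even PR, institutionally. Marrow progression is unattainable above 50% at entry, and at 50% it depends on whether the threshold is inclusive.

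The size is small. Part A response is descriptive and exploratory (11.5), few patients can be involved, and no dose conclusion depends on it. A reader might infer from Section 5.2 that these labels alone decide further cycles, or that the Part B result is exposed. Neither is supported: Section 10.1 gives other grounds for stopping, and Part B enrols osteosarcoma only, so its two-stage rule and error rates are unaffected. This is a minor correction worth making. The result rests on reading the categories literally and on treating all ten Curie sectors as graded 0 to 3.

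**What to change.** For response reporting only:

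1. In 12.4.3, add a separate reporting category for a relative score above 1.0 without new lesions, so that it is neither left blank nor counted as SD.
2. In 12.4.2, base the institutional report on the Curie score that sites are already asked to compute.
3. In 12.5.1, flag an increase in marrow tumor from an entry value where doubling is impossible as *increase, PD criterion not attainable* instead of plain SD. Leave unchanged or falling marrow as it is; making every high entry value inevaluable would also strip SD from stable or improving patients.
4. Add the matching rows to Tables 4 and 5.

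The sponsor must reconcile 12.3.5, 12.4.2, 12.4.3, 12.5.1 (including the inclusive versus strict sign in its examples), 5.2 and 10.1. No progression threshold or treatment rule is proposed here.

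The cost is wording: Curie scoring and marrow morphology are already specified. The downside is that a few patients may move out of SD in the descriptive tables.

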12.4.4 Overall Response Assessment

Table 5: Overall Response Evaluation for Neuroblastoma Patients and MIBG Positive Disease Only

If patients are enrolled without disease measurable by CT/MRI, any new or newly identified lesion by CT/MRI that occurs during therapy would be considered progressive disease.

MIBG	CT/MRI	Bone Scan	Bone Marrow	Catechol	Overall
PD	Any	Any	Any	Any	PD
Any	New Lesion	Any	Any	Any	PD
Any	Any	PD	Any	Any	PD
Any	Any	Any	PD	Any	PD
SD	No New Lesion	Non-PD	Non-PD	Any	SD
PR	No New Lesion	Non-PD	Non-PD	Any	PR
CR	No New Lesion	Non-PD	Non-PD	Elevated	PR

CR	No New Lesion	CR	CR	Normal	CR
----	---------------	----	----	--------	----

12.4.5 Overall Best Response Assessment

Each patient will be classified according to his “best response” for the purposes of analysis of treatment effect. Best response is determined from the sequence of the overall response assessments as described in Table 3 in [Section 12.6](#).

12.5 Response Criteria for Neuroblastoma Patients with Bone Marrow Involvement

12.5.1 Bone Marrow Involvement

Bone marrow obtained within 28 days prior to study enrollment with tumor cells seen on routine morphology (not by immunohistochemical staining only) of bilateral aspirate or biopsy on one bone marrow sample.

Bone Marrow responses are determined by H&E Staining of bilateral bone marrow biopsies and aspirates.

Complete Response: No tumor cells detectable by routine morphology on 2 consecutive bilateral bone marrow aspirates and biopsies performed at least 21 days apart. Normalization of urinary catecholamines or other tumor markers if elevated at study enrollment.

Progressive Disease: In patients who enroll with neuroblastoma in bone marrow by morphology have progressive disease if there is a doubling in the amount of tumor in the marrow AND a minimum of 25% tumor in bone marrow by morphology. (For example, a patient entering with 5% tumor in marrow by morphology must increase to $\geq 25\%$ tumor to have progressive disease; a patient entering with 30% tumor must increase to $> 60\%$).

In patients who enroll without evidence of neuroblastoma in bone marrow will be defined as progressive disease if tumor is detected in 2 consecutive bone marrow biopsies or aspirations done at least 21 days apart.

Stable Disease: Persistence of tumor in bone marrow that does not meet the criteria for either complete response or progressive disease.

